14.3.1 Informed Consent/Accent Process (in Case of a Minor)

If required by the site's IRB, the parent or legal guardian will sign a waiver of assent for the minor due to the study participant's age. Assent age will be determined by the local IRB. Appropriate documentation will be required for subjects who are the age of assent, whether mature enough to read and capable of providing signed assent, or whether too young to read but capable of providing verbal assent, as determined by the local IRB in compliance with 45CFR46. Local IRBs will review and assign the risk level.

14.4 Exclusion of Women, Minorities, and Children (Special Populations)

This study will be conducted solely in premature infants. The study will not exclude young children, females, or minorities.

14.5 Subject Confidentiality

The information obtained during the conduct of this clinical study is confidential, and disclosure to third parties other than those noted below is prohibited. The results of the research study may be published, but study participant's names or identities will not be revealed. Records will remain confidential. To maintain confidentiality, the principal investigators at each site will keep records in locked cabinets or locked rooms and the results of tests will be coded to prevent association with volunteers' names. Data entered into computerized files will be accessible only by authorized personnel directly involved with the study and will be encoded. Data received by DMID will not include subject specific data but only encoded data. However, subject specific information will be available to the clinical monitors, to the FDA and to health authorities where provided by law. .

The study investigator is obliged to provide the UAB Central Unit and NIAID/DMID with complete test results and all data developed in this study. The NIAID/DMID or UAB may disclose this information to appropriate regulatory authorities or clinical practice management groups (such as Pediatric Infectious Disease Society) as deemed necessary.

Subject-specific information may be provided to other appropriate medical personnel only with the study participant's parent/legal guardian permission. To ensure compliance with current ICH guidelines, data generated by this study must be available for inspection upon request by representatives of national and local health authorities, the NIAID/DMID, UAB Central Unit personnel, and the IRB/IEC for each study site.

14.6 Study Discontinuation

Therapy is not being provided by the study in this sampling trial. Therefore, there is no procedure for subjects to continue therapy if the study is discontinued.

14.7 Future Use of Stored Specimens

Some of the specimens obtained from study participants during this study will be stored indefinitely in the UAB Central Laboratory at the University of Alabama at Birmingham and may be used in future CMV research. These specimens will be labeled with a code number and not with the study participant's name. At the time of consent for study participation, study participant's parent/legal guardian will have the opportunity to either agree to have their specimens used in future CMV research or decline to have their specimens used in future CMV research. The study participant's parent/legal guardian will indicate his/her preference by initialing the appropriate line or checking the appropriate box of the Consent Form in the section entitled, "Future Use of Specimens". Non-protocol designated, future testing of samples will be performed only on samples from study participants who have consented for future testing of samples. These specimens will only be utilized to better understand the natural history of CMV

or improve diagnosis. Residual specimens from subject who decline future use will be destroyed after the study, final analysis and report writing is complete.

A repository for residual samples will be established according to OHRP guidelines ensuring that codes or other personally identifying links will not be distributed to future researchers.

The specimens will be stored indefinitely in the UAB Central Laboratory at the University of Alabama at Birmingham. CMV specimens from study participants will be labeled and coded without study participant's identifiers. If the study participant's parent/legal guardian has indicated in the signed consent form that he/she does not agree to allow the future use of specimens for future CMV research, then his/her child's specimens will be destroyed at the completion of the study.

15 DATA HANDLING AND RECORD KEEPING

The investigator is responsible to ensure the accuracy, completeness, legibility, and timeliness of the data reported.

Electronic case report forms (eCRFs) will be developed by the UAB Statistical and Data Coordinating Center. The eCRFs will be provided electronically by the UAB Central Unit. Original data will be recorded on source documents (e.g., medical records, research progress notes, Source Document Worksheets documenting research related procedures). The DMID 11-0067 DMP provides a description of how the system will function. Source Document Worksheets that mirror each data field on the eCRF will be available for use by sites as a tool to record and maintain data for each study participant enrolled in the study when other source documents are not used to collect original data. All source documents should be completed in a neat, legible manner to ensure accurate interpretation of data. When making a change or correction, cross out the original entry with a single line and initial and date the change. DO NOT ERASE, OVERWRITE, OR USE CORRECTION FLUID OR TAPE ON THE ORIGINAL. Specific guidance to investigators and study staff on making corrections to source documents and eCRFs will be provided in the MOP for this study.

Data recorded on the eCRF that differ from source documents must be explained on the Comments eCRF and in the subject's source documents.

15.1 Data Management Responsibilities

All eCRFs must be reviewed by the investigator's research team, under the supervision of the investigator, who will ensure that they are accurate and complete. All data must be supported by source documents, which will remain available for review by regulatory personnel and monitors. Adverse events must be graded, assessed for intensity and causality, and reviewed by the site investigator or designee.

Data collection is the responsibility of the clinical trial staff at the site under the supervision of the site PI. During the study, the investigator must maintain complete and accurate documentation for the study.

The UAB Central Unit and Statistical and Data Coordinating will be responsible for data management, quality review, analysis of the study data, and writing of the clinical study report. These tasks are detailed in the DMID 11-0067 DMP.

15.2 Data Capture Methods

Clinical and laboratory data will be entered into a 21 CRF Part 11 compliant electronic Data Entry System (eDES) provided by the UAB Statistical and Data Coordinating Center. The data system includes password protection and internal quality checks, such as automated range checks, to identify data that appear to be inconsistent, incomplete, or inaccurate.

15.3 Types of Data

Data for this study will include clinical laboratory, pharmacokinetic, and virologic results, and clinical and outcome measures (e.g., PK, weight, and virology).

15.4 Timing/Reports

There are no planned interim analyses or safety reviews for this trial. Stopping rules are detailed in Section 9.5. Following enrollment and PK assessments on the first four study subjects, safety and pharmacokinetic data will be summarized and reviewed by the Sponsor (e.g., the DMID medical officer and the DMID medical monitor), Protocol Chair, the UAB Central Unit, and an independent pharmacology monitor. The frequency of future data reviews will be determined at that time.

15.5 Study Records Retention

Records and documents pertaining to the conduct of this study, including source documents, consent forms, laboratory test results, and medication inventory records, must be retained by the investigator for at least 2 years following completion of the study. No study records shall be destroyed without prior authorization from the UAB Central Unit and NIAID/DMID. These documents should be retained for a longer period, however, if required by local regulations. It is the responsibility of the sponsor to notify the UAB Central Unit, which will notify the investigators, when these documents no longer need to be retained.

15.6 Protocol Deviations

Each investigator must adhere to the protocol as detailed in this document and agree that any changes to the protocol must be approved by the UAB Central Unit and NIAID/DMID prior to seeking approval from the IRB/IEC. Each investigator will be responsible for enrolling only those study participants who have met protocol eligibility criteria.

A protocol deviation is any noncompliance with the clinical trial protocol, GCP, or Manual of Procedures requirements. The noncompliance may be either on the part of the study

participant, the investigator, or the study site staff. As a result of deviations, corrective actions are to be developed by the site and implemented promptly.

These practices are consistent with ICH E6 GCP sections:

- 4.5 Compliance with Protocol, Sections 4.5.1, 4.5.2, and 4.5.3
- 5.1 Quality Assurance and Quality Control, Section 5.1.1
- 5.20 Noncompliance, Sections 5.20.1 and 5.20.2.

It is the responsibility of the site to use continuous vigilance to identify and report deviations within 1 business day of identification of the protocol deviation that increases subject risk. Deviations that do not increase subject risk can be reported within 5 business days of knowledge of the event. All deviations must be promptly reported to the UAB Central Unit. UAB will report all deviations to DMID in accordance with DMID's instructions.

All deviations from the protocol must be addressed in the source documents. A completed copy of the DMID protocol deviation form must be maintained in the regulatory file (Project Notebook or designated location) as well as in the subject's source documents. A log of protocol deviation will be maintained in the Project Notebook. Protocol deviations must be sent to the local IRB per the IRB's guidelines. The site PI/study staff is responsible for knowing and adhering to their IRB/IEC requirements.

16 PUBLICATION POLICY

Following completion of this study, the investigators are expected to publish the results in a scientific journal. All research reports and other publications resulting from the work completed in this protocol shall:

- Acknowledge the support of the National Institutes of Health whenever publicizing the results from this clinical trial in any media by including an acknowledgement substantially as follows:
 - Be submitted to the Project Director in the form of advance copies for review and comment prior to the publication to ensure appropriate coordination of the research results.
 - Be furnished in a list of publications resulting from the research as part of the annual progress report submitted to the principal investigator.

The International Committee of Medical Journal Editors (ICMJE) member journals have adopted a trials-registration policy as a condition for publication. This policy requires that all clinical trials be registered in a public trials registry such as ClinicalTrials.gov, which is sponsored by the National Library of Medicine. Other biomedical journals are considering adopting similar policies.

Unless exempted, this trial will be registered prior to enrollment of study subjects. It is the responsibility of the study's PI (e.g., [name]) to register the non-exempted trials and post results in compliance with Public Law 110-85, the Food and Drug Administration Amendments Act of 2007 (FDAAA).

Ganciclovir pharmacokinetics		X ^h		X ^{i,j}			
Virology blood specimens for CMV viral load ^k	X ^l	X ^l	X ^l	X ^l	X ^l	X ^{l,m}	X ^{l,n}
CMV detection from noninvasive urine specimen	X ^o	X ^o	X ^o	X ^o	X ^o	X ^o	X ^o
Ganciclovir dosing information	X ^p	X ^p	X ^p	X ^p	X ^p	X ^p	X ^p
PRBC transfusion assessment	X ^q	X ^q	X ^q	X ^q	X ^q	X ^q	X ^q

Assessment for AEs or SAEs		X	X	X	X	X	X
Total volume of blood required for study procedures	1.75 mL	0.5 mL	0.5 mL	0.5 mL or 1.5 mL ⁱ	0.5 mL	0.5 mL	0.5 mL

a) Data and specimens in this column to be captured if subject still receiving ganciclovir as clinical treatment

b) Gestational age at delivery, date of birth, day of life at initiation of IV ganciclovir therapy, gender, race, ethnicity, birth weight, weight at enrollment, length in centimeters at enrollment, reason ganciclovir being administered, ganciclovir dose and dosing frequency, manufacturer of the ganciclovir lot utilized at the treating facility, date ganciclovir therapy was initiated

c) Window: Birth through Study Assessment Day 3)

d) WBC with differential, hemoglobin, platelet count. Optional laboratory draws are not required by the protocol, and so no documentation on a source document will be required.

e) If being drawn for clinical reasons; any laboratory value obtained during the window will suffice, with an effort being made to capture the most abnormal value. Optional laboratory draws are not required by the protocol, and so no documentation on a source document will be required.

f) AST, ALT. Optional laboratory draws are not required by the protocol, and so no documentation on a source document will be required.

g) To be drawn on the calendar day that ganciclovir PKs are being drawn. Study related laboratory draws will be delayed or deferred if the investigator believes that obtaining them might increase subject risk. Additionally, a study-related laboratory specimen that is unevaluable due to clotting or laboratory related issues will not be repeated. If a study related laboratory draw is delayed or deferred, study staff will document this on a source document.

h) Ganciclovir concentrations will be obtained with one of the Study Assessment Doses 3, 4, 5, 6, 7, or 8 (Window: Study Assessment Day 1 through Study Assessment Day 5) at the following time points: 0h (immediately prior to IV ganciclovir dose; window: -15 min), 1h (immediately after the end of the IV ganciclovir dose; window: +15 min), 2-3h, 5-7h, and 10-12h; required amount of whole blood for plasma ganciclovir determination at each time point is 200 μ L (0.2 mL). Study related laboratory draws will be delayed or deferred if the investigator believes that obtaining them might increase subject risk. Additionally, a study-related laboratory specimen that is unevaluable due to clotting or laboratory related issues will not be repeated. If a study related laboratory draw is delayed or deferred, study staff will document this on a source document.

i) If desired by the treating physicians, ganciclovir concentrations may be obtained around one dose during the window at the following time points: 0h (immediately prior to IV ganciclovir dose; window: -15 min), 1h (immediately after the end of the IV ganciclovir dose; window: +15 min), 2-3h, 5-7h, and 10-12h; required amount of whole blood for plasma ganciclovir determination at each time point is 200 μ L (0.2 mL). Optional laboratory draws are not required by the protocol, and so no documentation on a source document will be required.

j) If subject weighs < 575 grams, the second set of PK draws cannot be performed (would exceed blood draw parameters of 7 mL/kg over 42 days)

k) To be obtained only once per study period; ideally, at least 72 hours should separate viral loads being obtained in different study periods

l) Required amount of whole blood for CMV PCR is 0.5 mL. Study related laboratory draws will be delayed or deferred if the investigator believes that obtaining them might increase subject risk. Additionally, a study-related laboratory specimen that is unevaluable due to clotting or laboratory related issues will not be repeated. If a study related laboratory draw is delayed or deferred, study staff will document this on a source document.

m) If subject weighs < 600 grams, the virology specimen for CMV viral load will not be performed (would exceed blood draw parameters of 7 mL/kg over 42 days)

n) If subject weighs < 650 grams, the virology specimen for CMV viral load will not be performed (would exceed blood draw parameters of 7 mL/kg over 42 days)

o) Urine collection will be non-invasive (e.g., bagged, indwelling foley catheter, excess clinical specimen, etc.). If urine is obtainable, it will be frozen and sent to the UAB Central Laboratory for processing. If an attempt to

obtain urine for CMV detection is unsuccessful, study staff will document the failed attempt on a source document.

p) mg/dose, dosing interval, subject weight

q) Once during each Study Period the study team will record the number of PRBC transfusions received by the study subject since enrollment (for the Period 1 documentation) or since the last recording (for documentation for Periods 2-7). A PRBC transfusion is defined as ≥ 10 mL/kg of PRBCs within a 24 hour period.

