2.3 Potential Risks and Benefits

2.3.1 Potential Risks

As a sampling study, the potential risks relate to blood draws (e.g., bruising at the site, infection, anemia possibly requiring packed red blood cell transfusion). Requiring a baby to be at least 500 grams at the time of study enrollment will ensure that blood volumes withdrawn will be acceptable by research standards. Additionally, virtually all of the subjects will have long-term intravenous access for clinical care, through which blood can be withdrawn without risk of discomfort from the needle stick or bruising at the site during or after the blood drawing and rarely an infection. Transfusions are expected in hospitalized premature infants. One study reported that extremely premature neonates receive an average of 5.2 ± 4.2 transfusions over a six week period.³¹ Other trials have reported similar numbers of transfusions in this population.^{32,33} It is possible that even higher numbers of transfusions might be experienced in the at-risk population in this sampling study since they are receiving the myelosuppressive drug ganciclovir as part of clinical care. Transfusions are not associated with long-term sequelae.³³ Nevertheless, throughout the conduct of this study, transfusion rates will be carefully monitored.

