Both whole blood for CMV PCR and urine for CMV assessment will be obtained serially through Study Assessment Period 7 as long as the subject is receiving intravenous ganciclovir therapy (that is, until the ganciclovir is permanently discontinued). These specimens will be used to determine viral load and, as indicated, ganciclovir resistance. At each sample collection time, urine will be split into two aliquots. These aliquots will be available for CMV detection as appropriate, based upon whole blood viral loads. Specimens will then be available for subsequent testing for ganciclovir resistance in the UAB Virology Resistance Laboratory. Since ganciclovir is a renally excreted drug, serum creatinine will be drawn for the research protocol on the day that the ganciclovir pharmacokinetic specimens are obtained in order to calculate creatinine clearance using a method such as the modified Schwartz formula, and thus correlate ganciclovir clearance with renal function. Otherwise, data from hematology assessments (WBC count and differential, hemoglobin, platelet count) and from chemistry labs (serum creatinine, ALT, and AST) will be recorded on the study case report forms each study assessment period if they are being obtained for clinical reasons, but will not be drawn only for the purposes of the study. Ganciclovir dosing information (mg/dose, dosing interval, and subject weight) will be recorded on the day of the pharmacokinetic blood draws. Once a subject is successfully enrolled into the study the ganciclovir dosing information (mg/dose and dosing interval) will be recorded from the start of clinical treatment of ganciclovir until date of enrollment. After enrollment ganciclovir dosing information (mg/dose and dosing interval) will be captured from Study Assessment Period 1 through the Study Assessment Period 7; as long as the subject is receiving intravenous ganciclovir therapy.

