If the subject continues to receive intravenous ganciclovir from Study Assessment Day 18 through Study Assessment Day 24 (Period 4), and at the request of the treating physician, an additional set of blood samples will be obtained for PK assessments if the subject is 575 grams or more at time of collection. The additional samples will be analyzed as they are received in the UAB Antiviral Pharmacology Laboratory and the results will be provided to the treating physician for information purposes. Specimens would be obtained around one dose administered during this window, using the same sampling times as with the first pharmacokinetic draws.

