5.1 Subject Inclusion Criteria

1. Signed informed consent from parent(s) or legal guardian(s)
2. Confirmation of CMV infection from urine, blood, or saliva by culture, shell vial, or PCR tests (local lab)
3. Receiving intravenous ganciclovir, prescribed by the patient's physician and anticipated to receive at least 3 more doses after consenting
4. < 32 weeks gestational age at birth
5. ≥ 500 grams at study enrollment

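### After the optional second PK set the Period 5 to 7 draw rules do not change, so study blood can reach 8.26 to 8.85 mL/kg against the protocol's own limit of 7 mL/kg

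*Protocol*

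**What the plan says.** Appendix A has a row headed "Total volume of blood required for study procedures". It gives 1.75 mL for Period 1, 0.5 mL for each later period, and 1.5 mL instead of 0.5 mL in Period 4 if the second PK set is taken.

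Three footnotes hold the total to 7 mL/kg over 42 days:

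- Footnote j, second PK set in Period 4: "If subject weighs < 575 grams, the second set of PK draws cannot be performed (would exceed blood draw parameters of 7 mL/kg over 42". Section 4 repeats the condition: "if the subject is 575 grams or more at time of collection".
- Footnote m, Period 6: "If subject weighs < 600 grams, the virology specimen for CMV viral load will not be performed".
- Footnote n, Period 7: "If subject weighs < 650 grams, the virology specimen for CMV viral load will not be performed".

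Sections 7.3.4 and 8.2.1.1 set no weight check for the Period 5 viral load. Before Period 6 the only weight rule on a viral-load draw is the entry criterion in Section 5.1, "≥ 500 grams at study enrollment". Section 2.3.1 offers as reassurance that being "at least 500 grams at the time of study enrollment will ensure that blood volumes withdrawn will be acceptable by research standards".

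On creatinine, Section 4 says "serum creatinine will be drawn for the research protocol on the day that the ganciclovir pharmacokinetic specimens are obtained". Section 8.2 puts that draw at 0.25 mL.

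**The concern.** The second PK set takes five samples of 0.2 mL. That extra 1.0 mL stays in the infant's 42-day total, so the weight needed for each later draw should rise. No text in either document raises a floor or drops a Period 5, 6 or 7 draw after a second set. A site can follow every footnote exactly and exceed the limit that the footnotes exist to enforce, with no deviation recorded.

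The infants concerned are the smallest in the study. Section 9 treats blood draws as the study's only risk, and Section 2.3.1 names anemia that may need transfusion among the consequences.

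**Working it through.** **Inputs.** Limit 7 mL/kg (footnotes j, m, n). PK set 5 × 0.2 = 1.0 mL, viral load 0.5 mL, creatinine 0.25 mL (Sections 7.2.1, 8.2, 8.2.1). Weight is taken at the time of the draw, as the footnotes do, and every earlier study sample is assumed taken.

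**Totals row.** Period 1: 1.0 + 0.25 + 0.5 = 1.75 mL. Period 4 with PK: 1.0 + 0.5 = 1.5 mL. Both reproduce.

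**Cumulative volume (mL)**

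| Period | 1 | 2 | 3 | 4 | 5 | 6 | 7 |
|---|---|---|---|---|---|---|---|
| No second set | 1.75 | 2.25 | 2.75 | 3.25 | 3.75 | 4.25 | 4.75 |
| Second set | 1.75 | 2.25 | 2.75 | 4.25 | 4.75 | 5.25 | 5.75 |

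**The stated floors.** Minimum weight in g = cumulative mL ÷ 7 × 1000. The second set needs 4.25 ÷ 7 = 607.1 g. Without a second set, Period 6 needs 607.1 g and Period 7 needs 678.6 g. The stated 575, 600 and 650 g do not reproduce. If the 0.25 mL Period 1 creatinine is left out, the minima become 571.4, 571.4 and 642.9 g, and 500.0 g for Period 5. These fit the stated floors and the entry weight, so omitting that draw is a plausible cause. The totals row nevertheless counts it.

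**Main check: after a second set, at weights the rules allow**

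| Draw | Weight | mL | mL/kg | Over by | Without Period 1 creatinine |
|---|---|---|---|---|---|
| Period 5 | 575 g | 4.75 | 8.26 | 0.725 mL (18%) | 4.50 ÷ 0.575 = 7.83 |
| Period 6 | 600 g | 5.25 | 8.75 | 1.05 mL (25%) | 5.00 ÷ 0.600 = 8.33 |
| Period 7 | 650 g | 5.75 | 8.85 | 1.20 mL (26%) | 5.50 ÷ 0.650 = 8.46 |

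The permitted weights that exceed the limit are 575–678 g in Period 5, 600–749 g in Period 6 and 650–821 g in Period 7.

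Correcting only the 575 g floor is not enough. At 608 g an infant is at 4.25 ÷ 0.608 = 6.99 after the set. At unchanged weight it reaches 4.75 ÷ 0.608 = 7.81 in Period 5 and 5.25 ÷ 0.608 = 8.63 in Period 6.

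**Smaller breaches**

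- Second set itself at 575 g: 4.25 ÷ 0.575 = 7.39, over by 0.225 mL.
- Period 6 at 600 g, no second set: 4.25 ÷ 0.600 = 7.08, over by 0.05 mL.
- Period 7 at 650 g, no second set: 4.75 ÷ 0.650 = 7.31, over by 0.20 mL.
- Period 5 at 500 g, no second set: 3.75 ÷ 0.500 = 7.50, over by 0.25 mL.

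**Period 4 creatinine.** Section 7.3.3 asks for creatinine when the second PK set is drawn. Appendix A marks the Period 4 creatinine as recorded only if clinically drawn, and the 1.5 mL leaves it out. If it is a study draw, cumulative volumes are 4.50, 5.00, 5.50 and 6.00 mL in Periods 4 to 7. That gives 7.83 and 8.70 mL/kg at 575 g (Periods 4 and 5), 9.17 at 600 g and 9.23 at 650 g.

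**Can growth absorb it?** An infant at 575 g at the second set must reach 679, 750 and 822 g for the Period 5, 6 and 7 draws, gains of 104, 175 and 247 g. From Day 21 to Days 28, 35 and 40.5 that is 14.9, 12.5 and 12.7 g/day. The figure depends on the days chosen: for Period 5 it runs from 104 ÷ 13 = 8 g/day (Day 18 to 31) to 104 g in one day (Day 24 to 25).

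**The case against.** The strongest case is that the breach is rare and small. It needs a physician-requested second set, all earlier samples taken, ganciclovir continued past Day 24, and weight still below 679, 750 or 822 g. Section 2.1 puts therapy for postnatal disease generally at two to four weeks, and four weeks ends by Study Assessment Day 28 at the latest. Periods 6 and 7, the source of 8.75 and 8.85, fall after that. Reaching 8.85 from 575 g means gaining only 75 g over 15 to 24 days, about 3 to 5 g/day. The largest excess is 1.20 mL, while the protocol expects up to five transfusions of at least 10 mL/kg per infant.

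There are other safeguards: deferral when a draw might raise risk (Section 5.3.2), the stop at 10 transfusions (9.3.1), the study-level halting rule (9.3.2), safety oversight (9.4), data review after the first four infants (15.4), and the SAP's monthly transfusion reports and transfusion alert.

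The rarity argument stands as to frequency, though the documents give no weight data to quantify it. The study also takes congenital infection (Section 11.1), for which Section 2.1 describes six-week courses, and the schedule itself plans draws through Day 42. The safeguards limit consequences, but none caps volume or requires a running total.

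Two further points are fair. The smaller breaches, 0.05 to 0.25 mL, all vanish if the Period 1 creatinine is not counted, and the 500 g case is avoided by a gain of about 1.5 g/day (36 g over 24 days). Section 2.3.1 also does not name 7 mL/kg, so reading its research standards as that limit is an assumption.

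**Conclusion.** The concern holds. After a second PK set, the Period 5 to 7 rules permit 8.26 to 8.85 mL/kg against a stated 7, an excess of 0.725 to 1.20 mL. The conclusion does not depend on how creatinine is counted: the lowest version is 7.83 to 8.46, and the highest, with a Period 4 study creatinine, is 8.70 to 9.23. These are worst cases at the permitted weights. An infant at or above 822 g in Period 7 (858 g with the extra creatinine) is within the limit at that draw. The volumes are the protocol's stated amounts; SAP Table 1 gives the PK and PCR volumes as minimums, so actual totals could be higher.

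The number affected is unknown and probably small, and the primary endpoint is untouched. A safety threshold that fails its own stated limit in the smallest infants must still be corrected. The slightly low floors and the missing Period 5 check would, on their own, be a lesser matter.

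**What to change.** First settle whether the Period 4 creatinine is a study draw, and bring Section 7.3.3 and Appendix A into line, because this decides the floors. Then make them depend on whether a second set was drawn (g, rounded up):

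| | Second set | Period 5 | Period 6 | Period 7 |
|---|---|---|---|---|
| No second set | – | 536 | 608 | 679 |
| Second set, Period 4 creatinine not a study draw | 608 | 679 | 750 | 822 |
| Second set, Period 4 creatinine a study draw | 643 | 715 | 786 | 858 |

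A simpler alternative is a bedside running tally of study blood, checked against 7 mL/kg at current weight before every draw. It covers every case with one rule. An eDES display could support it but not replace it, since SAP Sections 6 and 7 allow entry days after the visit or period end.

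The cost is one amendment: footnotes j, m and n; a Period 5 check in Section 7.3.4; the assurance in Section 2.3.1; the weights repeated in the Protocol Summary and Sections 4, 7.3.3, 7.3.5, 7.4.1, 8.2.1.1 and 8.2.1.2; and the matching footnotes to SAP Table 1. A few late viral-load or optional PK samples from the smallest infants would be lost.
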